6) Provide a statement of specific aims and hypotheses that serve as the basis for this protocol. Emphasize those aspects that justify the use of human subjects.

Aim 1: Investigate whether Computerized Executive Function Training (CEFT) leads to objective and subjective improvements in executive functioning and whether this in turn mediates PTSD symptom improvement.

Hypothesis 1a: CEFT will be associated with improvements in both objective and subjective executive functioning.

Hypothesis 1b: Enhanced executive functioning will mediate the relationship between treatment group and PTSD symptom improvement.

Aim 2: Investigate the efficacy of administering CEFT prior to Cognitive Processing Therapy (CEFT-CPT) in improving treatment adherence, completion rates, and outcomes in OEF/OIF Veterans with PTSD.

Hypothesis 2a: Individuals in the CEFT-CPT condition will have greater improvements in PTSD symptoms and quality of life than the control condition (placebo word training plus CPT).

Hypothesis 2b: Individuals in the CEFT-CPT condition will have higher rates of treatment engagement (i.e., completing more hours of homework and attending a greater number of sessions) and higher rates of treatment completion than those in the control condition.

Aim 3: Investigate whether functioning of brain regions in an EF network at baseline predicts treatment response.

Hypothesis 3: Dysfunction in a network of brain regions supporting EF will predict poorer response to treatment. Specifically, those who do not complete treatment and who demonstrate a poorer response will exhibit decreased connectivity between dorsolateral PFC and other regions, including anterior cingulate cortex and parietal cortex, compared to completers and better responders.

Section 7 - Background and Significance

7) Provide a succinct discussion of relevant background information to justify performing the proposed study.

PTSD affects approximately 14% of OEF/OIF Veterans and leads to considerable personal and societal costs (e.g., increased morbidity, reduced work productivity, poorer relationships). Cognitive behavioral therapy (CBT) has been shown to be one of the most effective treatments for PTSD. The Institute of Medicine

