Thus, the main goal of the proposed study is to examine whether administering computerized EF training (CEFT) immediately prior to CPT will improve executive functioning and enhance treatment adherence, completion rates, and psychological and functional outcomes in OEF/OIF Veterans with PTSD. Objective (neuropsychological) and subjective (self-report) measures of EF will be collected to determine if CEFT enhances EF and if this in turn mediates the relationship between treatment condition and PTSD symptom improvement. Functional neuroimaging during EF tasks will also be collected at baseline to determine whether functioning within an EF network predicts treatment response, above and beyond traditional paper-and-pencil measures of EF.

The proposed research aims to reduce barriers to treatment engagement and has potential to significantly enhance current treatments for PTSD by combining cognitive and psychotherapeutic approaches. Targeting EF directly and independently represents a logical, innovative, and empirically-informed method for augmenting existing treatments for PTSD in order to optimize outcomes. Findings from the study will not only directly inform clinical practice, but also have the potential to significantly reduce societal costs and burden, improve access to care, and reveal ways to better match individuals with treatments they are most likely to benefit from. Successful treatment of PTSD also reduces comorbidities including depression, substance use, and suicidality and improves the quality of Veterans' lives, including enhancing physical health, employment rates/work productivity, and interpersonal functioning.

Section 9 - Design and Methods

9) Describe the research design and the procedures to be used to accomplish the specific aims of the project. Provide a precise description of the planned data collection (include what systems or databases will be used/accessed to gather data), analysis and interpretation. For chart review studies, include the timeframe

of collection. Address sample size, inclusion of women and minorities. Define in clear terms exactly what will be done to the human subjects.

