Overview: The study is a randomized controlled trial (RCT) that will compare computerized EF training administered prior to CPT (CEFT-CPT) to a placebo word game training prior to CPT (WT-CPT). Goals of the research include 1) examining whether CEFT improves EF in OEF/OIF Veterans with PTSD and whether this in turn mediates PTSD symptom improvements, 2) investigating the efficacy of CEFT-CPT in improving treatment adherence, completion rates, and psychological and functional outcomes, and 3) determining whether baseline measures of EF predict treatment response. Veterans will be enrolled from the VASDHS system of PTSD clinics, spanning the main and 3 satellite facilities, and general outpatient mental health clinics. Assessments will be administered at baseline, immediately after CEFT or word training (prior to CPT), and after CPT completion.

Participants:

Inclusion criteria: 1) OEF/OIF Veterans enrolled at VASDHS, 2) aged 18-55 3) current PTSD diagnosis, 4) endorsement of cognitive complaints, 5) no pending medication changes, 6) English-speaking. Given the potential impact on outcome variables of interest, we will track current medication use in enrolled Veterans to ensure no recent or pending changes.

Exclusion criteria: 1) active substance use disorder in the last month, 2) suicidal intent or attempt within the last month, 3) schizophrenia, psychotic disorder and/or bipolar disorder, 4) dementia, 5) premorbid IQ < 70, 6) participation in other concurrent PTSD intervention studies, 7) previous completion of more than 4 CPT sessions, 8) history of a documented neurological disorder (e.g., Parkinson's disease, multiple sclerosis, epilepsy) 9) moderate to severe TBI (loss of consciousness greater than 30 minutes or post-traumatic amnesia greater than 24 hours).

Further exclusion criteria details: A history of mild TBI is highly comorbid in OEF/OIF but the majority of the literature supports a mental health etiology to persistent symptoms following mTBI; the current study will account statistically for mTBI history but it is not exclusionary.

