During recruitment, we will initially screen Veterans by phone. Those that are eligible for the study based on the phone screen will be brought to the lab for consenting, intake, and baseline assessments (approximately 200 Veterans). However, we assume a portion of those individuals will not qualify for the study. That will leave us with approximately 150 Veterans (75 per condition) to randomize to treatment. For recruitment, we will utilize the VASDHS system of PTSD clinics, spanning the main and 3 satellite facilities, and general outpatient mental health clinics. VA employees are not the target population, however they will not be excluded if they meet the inclusion criteria.

Financial Incentives: Participants will be compensated for their time after each completed assessment. Veterans will receive \$50 for the baseline assessment (\$30 for completion of the questionnaires and

neuropsychological assessment, \$20 for the fMRI assessment), \$30 as a bonus for completing at least 80% of the cognitive training (or placebo word games), \$50 for the post-computerized training assessment, and \$70 for the post-therapy assessment (Total possible = \$200).

Procedures:

Design and methods: Veterans will be randomized to either 12 weeks of CEFT-CPT or placebo word training plus CPT. Assessments will be administered three times: at baseline, immediately after CEFT or word training (prior to CPT), and after CPT completion. Assessment of PTSD diagnosis, symptom severity, quality of life, and subjective and objective measures of cognition will be administered at baseline (prior to computerized training onset), immediately after completing the cognitive training portion of the study (i.e., 6 weeks after baseline, just prior to starting CPT), and after completion of CPT treatment (approximately 6 weeks later, a total of 12 weeks after study initiation). Treatment satisfaction will be assessed after CEFT and CPT completion. Symptom severity will also be assessed at the midway point for the cognitive training and weekly during the CPT intervention component. Functional neuroimaging during rest and during two well-validated EF tasks will be collected at baseline, a Go-No Go Task that taps inhibition and an N-Back Task that taps working memory.

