Pre-study screening (15-30 minutes): Initial screening for interest and eligibility will take place in person or via telephone. Veterans will be given an overview of the study and, after providing verbal consent, will be screened with a questionnaire covering the major inclusion/exclusion criteria. Veterans who are not excluded based on the phone screening and who express interest in participating in the study will be invited to come to the VASDHS for continued evaluation of eligibility for participation in the study.

Baseline Assessment (4 hours): During the baseline appointment, Veterans will first provide written informed consent and HIPAA consent and then complete a structured clinical interview, the Clinician-Administered PTSD Scale for DSM-5 (CAPS-5) to determine PTSD diagnosis. Veterans will be then be assessed on a battery of self-report questionnaires to measure psychiatric symptoms and functioning including PTSD, depression, quality of life, and subjective EF in daily life (see measures section below). Objective cognitive functioning will be measured with standard neuropsychological tests in the domains of EF, verbal memory, attention/processing speed, and premorbid intellectual functioning. Multiple measures of EF will be administered that include tests of inhibition, working memory, and cognitive flexibility. The other cognitive domains assessed have also been associated with PTSD and may contribute to poorer EF (e.g., processing speed). Objective measures of effort will also be administered to assess validity of neuropsychological testing, in order to accurately interpret test scores/performances. All assessments will be administered by a trained research assistant.

Veterans who meet MRI safety criteria will also attend a separate 1-hour MRI appointment to collect functional neuroimaging data during two well-validated EF tasks. During this appointment, structural imaging data will also be collected for registration to the functional data. If Veterans do not meet MRI safety criteria, they will perform the two EF tasks during the baseline assessment appointment, as data from the behavioral tasks will still be analyzed even if the fMRI data is not available.

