Treatment Randomization: Following baseline assessment, participants will be randomized to the experimental (CEFT-CPT) or control condition (WT-CPT). A computer-generated randomization sequence will be provided by our statistical expert [name] (consultant). Randomization will be stratified by gender to ensure a balanced number of males and females are in each treatment group. Participants, the study assessor, and therapists will be blinded to the experimental treatment condition.

Post-Intervention Assessments (3-4 hours): The full battery of self-report questionnaires measuring psychiatric symptoms, quality of life, and subjective cognitive functioning, objective measures of neuropsychological functioning, and structured clinical interview for PTSD diagnosis will be re-administered twice, once after cognitive training completion and again after CPT completion. For the neuropsychological tests, alternate forms will be used where available and the RCT design will distribute any practice effects equally across the two groups. Participants will also complete the two EF tasks again that were administered at baseline during neuroimaging (though fMRI will not be collected again) or during the baseline assessment if they did not undergo fMRI for safety reasons.

Assessment Measures:

Symptom Measures:

- **PTSD:** The Clinician-Administered PTSD Scale DSM 5 (CAPS-5; Weathers et al., 2013) is the gold-standard, semi-structured interview that corresponds to DSM-5 criteria for PTSD. The CAPS-5 shows strong reliability and validity.

PTSD Checklist for DSM-5 (PCL-5; Weathers, Litz, Keane, Palmieri, Marx, & Schnurr, 2013) will be used to regularly assess PTSD symptomatology at several points throughout the study. The PCL-5 is a 20-item self-report measure of PTSD symptoms with good psychometric properties. The PCL-5 maps directly onto DSM-5 diagnostic criteria.

- **Depression:** Beck Depression Inventory-II (BDI-II; Beck, Steer, & Brown, 1996) is a 21-question multiple-choice self-report inventory, one of the most widely used instruments for measuring depressive symptoms.
- **Subjective day-to-day executive functioning:** Behavior Rating Inventory of Executive Function (BRIEF; Guy et al., 2004) is an ecologically sensitive 75-item self-report questionnaire that measures several aspects of EF in an individual's everyday life in the last month, including inhibition, shifting, working memory, planning/organizing, emotional control, etc.

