- **Client Satisfaction with Treatment:** Client Satisfaction Questionnaire (CSQ; Attikisson & Zwick, 1982) is an 8-item self-report scale measuring satisfaction with treatment. It has excellent internal consistency and correlates with therapists' estimates of client satisfaction. This instrument will be used to measure participants' satisfaction with the interventions.
- **Homework Compliance:** Homework Compliance Scale (HCS; Primakoff et al., 1986) is a single item questionnaire in which participants rate their degree of homework compliance on a scale from 0 (homework was not assigned) to 6 (I did more of the assigned homework than requested). An estimate of the number of minutes spent completing homework since the previous session and number of completed worksheets and assignments will also be recorded at each CPT session.
- **Alcohol Screening Tool:** The Alcohol Use Disorders Identification Test-C (Audit-C; Saunder et al., 1993) is a 3-item screening measure used to screen for alcohol use disorder, which is an exclusion criteria for the study.

Neuroimaging: Collected only at baseline

Experimental fMRI Tasks:

N-Back Working Memory Task: In this task, pseudo-words are presented on each trial and the participant must determine whether the current stimulus matches the one n-back. There are 3 types of n-backs in the task: 1-back, 2-back, and 3-back. Participants respond via a keystroke whenever they see a pseudo-word repeated either one, two, or three pseudo-words back. Each participant will receive a practice block before going into the scanner and two blocks while in the scanner, with each block containing all 3 N-back conditions in an alternating order. Reaction time and accuracy on each trial are recorded during scanning.

Go-No Go Inhibition Task: In this task, shapes are presented on screen. Participants are instructed to make a button press to every shape except when a circle or square appears on screen. Each participant will receive a practice block before going into the scanner and two blocks while in the scanner. Reaction time and accuracy on each trial are recorded during scanning.

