2. Auditory Ace: auditory working memory exercise, essentially an N back task where auditory information is retained and manipulated to determine if the current card matches a card N steps back in the sequence
3. Card Shark: visuospatial working memory exercise, similar to the Auditory Ace, except the information used to determine matches is presented visually
4. Juggle Factory: visuospatial working memory exercise, participants reconstruct a sequence of numbers in moving circles in the correct order, at more difficult levels participants must inhibit the influence of distractors
5. Mixed Signals: inhibition exercise, participants respond if what they hear and see matches in a particular way (while ignoring irrelevant information), otherwise they withhold their response
6. Divided Attention: inhibition exercise, participants indicate whether two objects match on a particular aspect (e.g., shape, color, fill) while ignoring irrelevant/competing aspects

Placebo word games: Participants in the active control group will be assigned to complete computerized placebo game training at the same frequency as CEFT. *Games and puzzles will be accessed online via BrainHQ in a similar manner to the CEFT condition.* This placebo condition controls for the effects of computer exposure, contact with research staff, and monetary payments. In addition, it controls for nonspecific engagement and motivation through the reinforcement of graphics-based computer games but does not provide the constrained, intensive, adaptive training of specific executive functions that the active condition provides. Participants will rotate through a series of games (e.g., *sudoku*, *crossword*, *connect four*) for the same number of hours as the EF training condition. After 6 weeks of game training, they will also receive CPT-C as detailed below.

Cognitive Processing Therapy: CPT is an evidence-based, trauma-focused therapy for PTSD endorsed by the VA/DoD Practice Guidelines and is widely available within VASDHS. Patients will receive a well-validated version of CPT, CPT-Cognitive only (CPT-C), which is a standard PTSD treatment provided at the VA that differs from the original version of CPT in that it does not include written trauma accounts. It entails 12 visits to the VA, each lasting 50 minutes.

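### Do the repeated N-Back and Go-No Go tasks, whose format the active training partly shares, need a declared role to protect Hypotheses 1a and 1b?

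*Combined protocol and SAP*

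**What the plan says.** All places are in the combined protocol and SAP.

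- **Repeat testing.** Section 9, Post-Intervention Assessments, has the questionnaires, neuropsychological tests and PTSD interview given again twice, then adds: "Participants will also complete the two EF tasks again that were administered at baseline during neuroimaging". No imaging is repeated.
- **Baseline role of the tasks.** Aim 3 in Section 6 is to "Investigate whether functioning of brain regions in an EF network at baseline predicts treatment response". The Section 9 Overview gives the matching goal as "determining whether baseline measures of EF predict treatment response". Design and methods describes the tasks as "a Go-No Go Task that taps inhibition and an N-Back Task that taps working memory".
- **Measures for EF change.** Section 7 says: "Objective (neuropsychological) and subjective (self-report) measures of EF will be collected to determine if CEFT enhances EF". The EF tests listed in Section 9 under objective neuropsychological testing are the WCST, D-KEFS Color-Word Interference and Trail Making, and the PASAT. N-Back and Go-No Go are not listed there. They are described under Neuroimaging, as experimental fMRI tasks.
- **Behavioral data.** The Baseline Assessment paragraph says that "data from the behavioral tasks will still be analyzed even if the fMRI data is not available". The task descriptions add: "Reaction time and accuracy on each trial are recorded during scanning".
- **Training content.** The BrainHQ list has six modules, including "Auditory Ace: auditory working memory exercise, essentially an N back task". Card Shark is its visual counterpart. Mixed Signals requires a response on a match between sound and picture, and withholding otherwise. The control games are described as lacking intensive, adaptive training of specific executive functions.
- **Analysis.** The Data Analysis text gives a multilevel model with group, time and their interaction. It names no EF outcome for Hypothesis 1a and no mediator for Hypothesis 1b.

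**The concern.** The repeat scores have no stated purpose. Aim 3 uses baseline data only, and Aim 2 concerns symptoms, quality of life, engagement and completion. Aim 1, on EF change, is thus the one aim the repeat scores could obviously serve, and its hypotheses name no instrument.

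The active arm also practices a format on which it is later tested. The protocol's remark that randomization spreads practice effects evenly is made about the neuropsychological tests and holds for retest practice. It cannot balance practice that one arm receives as its treatment. If the N-Back score served as the objective half of Hypothesis 1a, or as the mediator in Hypothesis 1b, a gain from familiarity with the format could be read as a general EF gain.

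**Working it through.** **1. Which measures does the text assign to EF change?**

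| Place | What it implies |
|---|---|
| Section 7 | Objective EF means neuropsychological measures; this is the sentence tied to the Aim 1 question |
| Section 9, Baseline Assessment | Objective cognition, EF included, is measured with standard neuropsychological tests |
| Section 9, Assessment Measures | Four EF tests listed; the two tasks absent |
| Section 9, Neuroimaging | The two tasks described here, as fMRI tasks |
| Section 9, Post-Intervention Assessments | Neuropsychological measures named first; the two tasks added in a separate sentence |

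All five point the same way. The promise to analyze behavioral data explains why Veterans who cannot be scanned do the tasks at the baseline visit. It does not assign the repeat scores to Aim 1.

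**2. How large is the overlap?** The N-back format is explicit in 2 of 6 modules (Auditory Ace and Card Shark). Mixed Signals is similar to Go-No Go only in function: its rule combines sound and picture, whereas the tested task is visual and asks for a press to every shape except two. Stimuli differ throughout; the tested N-Back uses pseudo-words.

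Planned training time is 0.5 h × 5 days × 6 weeks = 15 h. The documents do not split it by module. If the split were equal (an assumption), N-back modules would take 15 × 2/6 = 5 h and Mixed Signals 15 × 1/6 = 2.5 h.

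**3. How many scores are involved?** The main battery is repeated twice, but the sentence on the two tasks says only that they are done again. With 150 randomized, that gives 150 × 1 = 150 to 150 × 2 = 300 repeat administrations of each task, before attrition.

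**4. What would misuse cost?** The documents give no alpha, effect size or SD, so there is no figure of the plan's to reproduce. As an illustration, assume a two-sided 5% test, no true general EF gain, and a format-practice advantage of d SD in the active arm. With n analyzed per arm, the chance of a significant difference on one task is about Φ(d√(n/2) − 1.96). At n = 75, √37.5 = 6.12.

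| d (assumed) | n = 75 | n = 50 |
|---|---|---|
| 0.2 | 0.23 | 0.17 |
| 0.3 | 0.45 | 0.32 |
| 0.5 | 0.87 | 0.71 |

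If the two tasks were instead averaged with the four listed tests at equal weight, and only these two carried the advantage, the composite effect is (2d/6)/√((1 + 5r)/6), where r is the inter-test correlation. For d = 0.5:

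- r = 0.3: 0.167/0.645 = 0.258, probability 0.35.
- r = 0.5: 0.167/0.764 = 0.218, probability 0.27.

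These are costs of a use that step 1 does not support. They do not describe the plan as written.

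**5. What would a change add?** A sentence resting objective EF on the listed tests would repeat step 1. A sentence barring the two tasks from Aim 1 would draw a line of degree: CEFT targets inhibition, shifting and working memory, and the listed tests measure those same functions.

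**The case for a change.** The strongest case for a change is that nothing expressly excludes the two tasks. The protocol calls them EF tasks, describes them by functions it also lists for EF measurement, promises to analyze their behavioral data, and leaves the Aim 1 outcome and mediator unnamed. An analyst could choose among scores after seeing the data. Two sentences would close that door without touching assessments, training or sample size.

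Part of this stands. The repeat scores have no written role, the N-back overlap is in the protocol's own words, and the practice-effect remark does not reach it.

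Three things weaken it as a reason to amend:

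- The open choice belongs to a wider gap. No score or composite is chosen among the four listed tests either, and two sentences about N-Back and Go-No Go would leave that untouched. Naming the Hypothesis 1a outcome and the Hypothesis 1b mediator would settle these tasks in passing.
- Hypothesis 1a also requires subjective improvement, so a task gain alone could not confirm it.
- Barring the tasks is a preference. Keeping them as secondary measures of whether training engaged its target is defensible, and the overlap then affects interpretation without making the analysis wrong.

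**Conclusion.** No change is needed. This is missing detail that the surrounding text already steers: objective EF for Aim 1 rests on the neuropsychological tests, and the two tasks belong to the imaging aim. A sensible analyst would report their repeat scores separately, as near-transfer or target-engagement measures, and would mention the N-back overlap when interpreting an arm difference.

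The explicit overlap is 2 of 6 modules, with a third similar only in function. Any resulting bias cannot be sized from the documents, and the probabilities above depend on assumed practice effects, alpha and correlations. The conclusion rests on reading Section 7, the Baseline Assessment paragraph and the list of EF tests together as defining objective EF. It would not hold if the sponsor intended the repeated tasks as the Hypothesis 1a outcome or the Hypothesis 1b mediator, but the text gives no sign of that.
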